4.2.4. Safety Endpoints

The incidence, severity, relationship and type of TEAEs, SAEs, AEs leading to discontinuation of investigational drug, and AEs of special interest; clinically meaningful changes from baseline for clinical laboratory measures, vital signs, electrocardiograms (ECGs), and physical examination will be assessed.

Safety assessments will include the following:

- Collection of AEs
- Physical examinations
- Vital sign measurements
- ECG results
- Optical coherence tomography
- Pulmonary function tests (PFTs) (FEV₁, FVC, and diffusion capacity of the lung for carbon monoxide [DLCO], where available)
- Clinical laboratory tests

[REDACTED]

[REDACTED]

[REDACTED]

[REDACTED]

5. GENERAL STATISTICAL CONSIDERATIONS

All efficacy and safety data will be listed by patient. Listings will be sorted by patient number and visit/study day.

Continuous data will be summarized using descriptive statistics: number of patients (n), mean, standard deviation (SD), standard error (SE), median, minimum and maximum.

Categorical data will be summarized using the number and percent of patients. When count or frequency data are presented, the percent will be suppressed when the count is zero in order to draw attention to the non-zero counts. A row denoted “Missing” will be included in count tabulations where necessary to account for dropouts and missing values. The denominator for percentages will be the number of patients within the population of interest, unless otherwise stated. Denominator for percentages in demographic and baseline categories will use the number of non-missing values. Non-zero percentages will be rounded to one decimal place, except 100% will be displayed without any decimal places.

Additional rounding rules are as follows:

- If the original value has 0 decimal places: mean, median, and CIs will have one decimal place and SD will have 2 decimal places;
- If the original value has 1 decimal place: mean, median, and CIs will have 2 decimal places and SD will have 3 decimal places; and
- If the original value has 2 or more decimal places: mean, median, CIs, and SD will all have 3 decimal places.

Minimum and maximum will always have the same decimal places as the original measure, up to a maximum of 3 decimal places.

Unless otherwise indicated, values that are collected with “<” sign and a numerical bound will be analyzed as half the numerical bound, without the sign in tables and figures. Values that are collected with “>” sign and a numerical bound will be analyzed as the numerical bound, without the sign. In listings, these data will be reported as collected, with the sign.

5.1. Sample Size

The sample size of approximately 60 patients for the Induction Period has been chosen to enable estimates of response and remission rates with reasonable precision. To give this some context, if we assume a remission rate of 15% and a response rate of 30%, it is estimated that half-width of the 95% CI around the proportion of patients in response and remission, respectively, would be 12.8% and 16.4% for a 30 patient study. For a 60 patient study, on the other hand, the same half-widths would be 9.0% and 11.6%.

5.2. Randomization, Stratification, and Blinding

This is a non-randomized, unstratified, unblinded, single-arm, open-label trial.

5.3. Statistical Hypotheses and Multiple Endpoint Handling

No statistical hypothesis testing will be performed in this trial.

5.4. Analysis Populations

All patients who are enrolled in the Induction Period and receive at least one dose of investigational drug will comprise both the Intent-to-Treat (ITT) population and the Safety population. Because this is a single arm open label study, these two analysis populations are indistinguishable. This population will be used to summarize all efficacy and safety data for both Induction and Extension Periods.

5.5. Other Important Considerations

5.5.1. Definition of Baseline

Unless otherwise specified, baseline is defined as the last observation collected on or before the receipt of first dose of Investigational Product (IP). Calculation of Change and Percent Change from Baseline are done according to the following:

- Change from Baseline to any trial Week t (C_t) is calculated as follows:
 - $C_t = M_t - M_B$, where:
 - M_t is the measurement of interest at Week t
 - M_B is the measurement of interest at Baseline
- Percent change from Baseline to any trial Week t (P_t) is calculated as follows:
 - $P_t = 100 * (C_t / M_B)$

NOTE: If $M_B = 0$ or missing then percent change from Baseline will not be determined.

5.5.2. Study Day Calculation for Reporting Purposes

The following conventions will be used to calculate study day for reporting purposes:

- Study Day = date of measurement – first dose date +1, if date of measurement is on or after the first dose date.
- Study Day = date of measurement – first dose date, if date of measurement is prior to the first dose date.
- Study Day 1 is the first dose date of the Induction Period, and no Study Day 0 is defined.

5.5.3. Visit Windows

The analysis time point assignment for the post-baseline visits will be assigned based on the analysis windows described in [Table 4](#) below for the following items:

- Efficacy (please see Protocol Table 2 for a description of what study elements are considered to belong to the Efficacy category; it is also noted that not all Efficacy elements are considered in this SAP, please see the endpoints in Sections 4.2.2, 4.2.3, and 12)
- 12-lead ECG
- Vital signs
- Hematology
- Blood chemistry
- Pregnancy test
- Urinalysis
- Physical examination
- Pulmonary function test
- Optical coherence tomography

Adverse events and coagulation panel data will not be windowed.

If multiple assessments are available within a range, then the one closest to the target day will be used for that analysis time point. If multiple assessments are same distance, but on different sides of the target day, then the latter one will be used. If multiple assessments are available on the same day, then the average of these assessments will be used, except for the lab and ECG data for which the assessment at a later time of the same day will be used.

Table 4. Analytic Visit Windows

Visit	Ideal Analysis Day^a	Visit Window
Baseline	1	<= 1
Week 4	29	2 – 42
Week 8	57	43 – 70
Week 12	85	71 – 98
Week 24	169	99 – 210
Week 36	253	211 – 294
Week 48	337	295 - 350
Week 52	365	351 - 392
Week 64	449	393 - 490
Week 76	533	491 - 574
Week 88	617	575 - 658

Week 100	701	659 - 742
Week 112	785	743 - 826
Week 124	869	827 - 910
Week 136	953	911 - 994
Week 148	1037	995 - 1078
Week 160	1121	≥ 1079
Safety Follow-up Day 30	30	≤ 60
Safety Follow-up Day 75 and Day 90	90	≥ 61

^aExcept for the visits recorded as safety follow-up visits, the reference date will be the date of the first dose of IP in the study, and the relative day is calculated date of assessment/collection – date of the first dose of IP + 1 if the date of assessment/collection is on or after the date of the first dose of IP, or date of assessment/collection – date of the first dose of IP if the date of assessment/collection is before the date of the first dose of IP. The reference date for the visits recorded as safety follow-up visits will be the date of the last dose of IP in the study, and the relative day is calculated date of assessment/collection – date of the last dose of IP.

Applying above visit window rules will be done after distinguishing treatment visits and follow-up visits by CRF visit labels.

For all study elements to which the above table applies, the last available assessment will be derived as the last value on treatment, whether scheduled or unscheduled.

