12.1.10. Clinical Laboratory Evaluations

The central laboratory will analyze the samples. Further details of the procedures to be followed for sample collection, storage, and shipment will be documented in a laboratory manual.

Additional and repeat laboratory safety testing may be performed at the discretion of the Investigator.

- Hematology - RBC count, total and differential WBC count (basophils, eosinophils, lymphocytes, monocytes, and neutrophils), platelet count, mean platelet volume, hemoglobin, hematocrit, mean corpuscular volume, mean corpuscular hemoglobin, and mean corpuscular hemoglobin concentration. Total WBC and all differential WBC counts will be provided to the site in this open-label trial.

During the treatment period, WBC differential results will be available to the Investigator. Reductions in ALC levels is a known pharmacodynamic effect of RPC1063. If any of the following results are observed, the Investigator will be asked to repeat the laboratory tests within approximately 7 days:

- Absolute neutrophil count [ANC] < 1000 cells/ μ L
- Absolute lymphocyte count [ALC] < 200 cells/ μ L

If the ANC is confirmed below the acceptable limits, the Investigator will be requested to closely monitor for risk of serious infection and institute appropriate follow-up, at the discretion of the Investigator.

If the ALC is confirmed below the 200 cells/ μ L, the Investigator will temporarily discontinue investigational drug and then consult with the Medical Monitor. Laboratory testing will be repeated weekly until ALC is > 500 cells/ μ L.

When ALC has returned to > 500 cells/ μ L, treatment may be reinitiated at Investigator's discretion (Section 9.1.1 for instructions on resuming treatment after missing doses). For patients whose ALC level is confirmed < 200 cells/ μ L and has not reached the acceptable range (ALC > 500 cells/ μ L) during the study, laboratory testing will be repeated at the 90-day Safety Follow-up Visit.

- Chemistry
 - Full chemistry panel at Screening: sodium, potassium, chloride, calcium, magnesium, phosphate, blood urea nitrogen, glucose, albumin, alkaline phosphatase, creatinine, SGPT/ALT, SGOT/AST, GGT, amylase, total bilirubin, conjugated bilirubin, total cholesterol, triglycerides, HDL and LDL, C-reactive protein.
 - All other visits - blood urea nitrogen, albumin, alkaline phosphatase, creatinine, ALT, AST, GGT, amylase, total bilirubin, conjugated bilirubin, C-reactive protein

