 - Any condition that might affect the outcome of pulmonary function testing including infection, respiratory symptoms, occupational exposures (including asbestos) and cigarette smoking needs to be collected before PFT testing and transcribed to the pulmonary function tests eCRF page. If patients have decline in PFT values (FEV1 and/or FVC) below 50% of the predicted values, treatment should be discontinued. If a patient discontinues due to respiratory AE, the Investigator should ensure that the patient has adequate evaluations as clinically indicated by a pulmonologist (consider PFTs, chest X-ray or high resolution computed tomography, based on findings of the other exams) at the time of the AE. For patients with pulmonary nodules, lung biopsy should be considered (Cryptococcus pneumonia and pulmonary TB have been reported with fingolimod). Further evaluations will be conducted until such time as resolution is confirmed or no further improvement is expected by the Investigator (based on a follow-up period of not less than 3 months).
- Hepatic effects
 - If patients have elevations in the LFTs (ALT or/and AST) \geq 3x ULN, a retest should be performed as soon as possible but not later than 14 days after the original test. If the abnormality is confirmed, weekly testing should continue until ALT and AST are $<$ 3x ULN. If the ALT and/or AST stabilizes at a level $>$ 3x ULN, the Medical Monitor may agree to less frequent testing. The Investigator should establish causality.
 - At any time, if any of the following occur and there are no apparent alternative causes for the finding, the investigational drug must be permanently discontinued:
 - ALT or AST $>$ 8x ULN or
 - ALT or AST $>$ 5x ULN with confirmation, within 2 weeks or
 - ALT or AST $>$ 3x ULN and (total bilirubin $>$ 2x ULN or INR $>$ 1.5) or

- ALT or AST > 3x ULN with the appearance of fatigue, nausea, vomiting, or right upper quadrant pain or tenderness, fever, rash and/or eosinophilia (>5%)

Investigator should establish causality.

After discontinuation due to elevation of ALT or AST > 5x ULN or concurrent elevations of ALT or AST > 3x ULN and bilirubin > 2x ULN, further liver function evaluation should be performed (for example, coagulation panel and alkaline phosphatase) in consultation with the Medical Monitor.

- Evaluation of alternative causes for the liver test abnormalities could include any of the following:
 - Acute viral hepatitis
 - Alcoholic or autoimmune hepatitis

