10.2.1. Hematology

The following laboratory tests will be included in hematology summary tables:

- Absolute Lymphocyte Count
- Basophils
- Basophils/Leukocytes
- Eosinophils
- Eosinophils/Leukocytes
- Ery. Mean Corpuscular HGB Concentration
- Ery. Mean Corpuscular Hemoglobin
- Ery. Mean Corpuscular Volume
- Erythrocytes
- Hematocrit
- Hemoglobin
- Leukocytes
- Lymphocytes
- Lymphocytes/Leukocytes
- Mean Platelet Volume
- Monocytes
- Monocytes/Leukocytes
- Neutrophils
- Neutrophils/Leukocytes
- Platelets

Actual values, change from baseline, and percent change from baseline will be summarized by visit. Shift tables from baseline, by visit, will be presented. The proportion of patients with abnormalities in Absolute Lymphocyte Count (ALC; $ALC < 200$ cells/uL; $ALC < 500$ cells/uL), Absolute Neutrophil Count (ANC; $ANC < 1000$ cells/uL), and Total WBC ($WBC > 20,000$ cells/uL) will be presented overall and by visit.

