APPENDIX 5. DOCUMENT REVISION HISTORY

Version	Date	Notes/Revisions
1.0	March 03 2016	Initial version.
1.1	November 23 2016	Updated with details and additional analyses.
1.2	January 26 2017	Updated with details on missing data and other details.
1.3	June 1, 2018	
Updated to reflect the Week 12 and Week 52 summary tables generated for topline analyses, definition of treatment failure, as well as to reflect endpoint alterations and additional details regarding CDAI, SES-CD, GHAS, and RHI algorithms. Analysis of compliance rate categories has been excluded.
 
Following endpoints have been removed from the SAP
 
 • PRO CD SF+AP response-25 • PRO CD SF+AP response-50 • PRO CD SF+AP response-30 + 2P • PRO2 CD response-25 • SF&AP clinical response-2 • SF&AP clinical response-1 • Endoscopic remission-2 • Histologic improvement • Histologic response 
Following endpoints have been added to the SAP
 
 • CRP-response-10 • FCP response-250 • Fistula Response • GHAS Improvement • GHAS Remission • RHI Improvement • RHI Response • RHI Remission • Global RHI Score • RHI Mucosal Healing
1.4	August 28, 2019	
LOCF removed.
 
Treatment Failure rule is used in NRI
 
Efficacy graphs added

1.5	January 06, 2020	
Changes from data review meeting
 
 • PFT abnormality has been revised • Missing segment imputation of SES-CD has been added

		
• Lower bound of 0 for Hematocrit sub-score of CDAI has been added• Treatment failure criteria has been revised• RHI response analysis on all patients has been removed• RHI remission by segment for subset of segment score > 3 is replaced by RHI remission by segment for non-RHI remitters• CRP Change among patients having CRP \geq 10 mg/L at Baseline has been added• Analysis window has been added to Safety follow-up visits• Unscheduled and early termination visits are included in all analysis windows• Patients requiring cardiac monitoring is determined programmatically• Listing of non-trial procedures added• Section on PK analysis is removed and combined with Section on PD• Description of SDTM data in Section 5 is removed
--	--	---

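### In by-visit lab tables a required retest can replace an abnormal scheduled value, and five analysis windows have no scheduled lab draw to fill them

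*SAP*

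**What the plan says.** **Selection rule.** SAP 5.5.3 lists hematology and blood chemistry among the windowed data. When a window holds several values, "If multiple assessments are available within a range, then the one closest to the target day will be used for that analysis time point". For ties, "If multiple assessments are same distance, but on different sides of the target day, then the latter one will be used". Nothing favours the scheduled draw or the worst value.

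**What enters the windows.** The version 1.5 entry in SAP Appendix 5 says "Unscheduled and early termination visits are included in all analysis windows". SAP 10.2 says that unscheduled lab results go to listings and to the highest, lowest and last value tables. It neither includes them in by-visit tables nor excludes them.

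**Retests.** Protocol 12.1.10: for ANC below 1000 or ALC below 200 cells/μL, "the Investigator will be asked to repeat the laboratory tests within approximately 7 days". After ALC is confirmed low, drug is held and "Laboratory testing will be repeated weekly until ALC is > 500" cells/μL. Protocol 12.2.7: for ALT or AST at or above 3x ULN, "a retest should be performed as soon as possible but not later than 14 days after the original test". It continues: "If the abnormality is confirmed, weekly testing should continue until ALT and AST are" below 3x ULN.

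**Tables affected.** Under SAP 10.2.1 the ALC, ANC and WBC abnormality proportions "will be presented overall and by visit". SAP 10.2.2 plans the same for ALT and AST. Neither section defines the overall figure.

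**Windows and schedule.** SAP Table 4 has windows at Weeks 64, 88, 112, 136 and 160. The hematology and chemistry rows of Protocol Table 3, as extracted, are blank at those weeks.

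**The concern.** The required retests are triggered only by abnormal results. A rule that picks by calendar distance alone can therefore drop the abnormal scheduled value and keep the retest. For the threshold that triggered the retest, this exchange can lower the by-visit count or leave it unchanged, but cannot raise it.

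At the five weeks without a scheduled draw, any value comes from an unscheduled test or an exit visit. The row then describes a selected subset under a heading that reads like a routine visit.

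Longer-term safety is the primary objective of the Extension Period, and ALC and liver enzymes carry protocol action thresholds. By-visit tables for these labs should mean what their headings say.

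**Working it through.** The plan gives no figure of its own on this point, so the check applies its rule to every permitted visit day.

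**Inputs.**
- SAP Table 4 target days all equal 7 × week + 1 (Week 24: Day 169).
- Protocol Tables 2 and 3 set visits at 7 × week. Lab visits at Weeks 4, 8, 12, 48 and 52 are ±3 days; those at Weeks 24, 36, 76, 100, 124 and 148 are ±7 days. So 5 of the 11 scheduled post-baseline lab visits are ±3.
- Retest lags are those of Protocol 12.1.10 (about 7 days) and 12.2.7 (at most 14 days). Shorter lags are allowed.

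**Rule.** Let x be the scheduled draw day minus the target day, and L the retest lag. The retest wins if |x + L| ≤ |x|, that is, if x ≤ −L/2. A visit on or after target is never replaced.

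**Range of x.** If protocol days are study days, x runs from −8 to +6 (±7 visits) or −4 to +2 (±3 visits). If they are elapsed days, it runs from −7 to +7 or −3 to +3. The table spans both readings.

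| Lag L | Condition | ±7-day visits | ±3-day visits |
|---|---|---|---|
| 1 day | x ≤ −0.5 | 7-8 of 15 | 3-4 of 7 |
| 3 days | x ≤ −1.5 | 6-7 of 15 | 2-3 of 7 |
| 7 days | x ≤ −3.5 | 4-5 of 15 (27-33%) | 0-1 of 7 (0-14%) |
| 14 days | x ≤ −7 | 1-2 of 15 (7-13%) | 0 of 7 |

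**Values taken during a drug hold.** Drug is held only after the retest confirms low ALC, so the first hold value comes at L + 7. It must be at least as close to target as both earlier values, so x ≤ −(L + 3.5) and x ≤ −(L + 7)/2. At ±7-day visits this is met on 3-4 of 15 days for L = 1, on 1-2 of 15 for L = 3, and on none for L = 5 or 7. At ±3-day visits it is not met for any of these lags.

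**Effect on a rate.** The fall equals p × u × f: the true by-visit rate, the share of retests no longer abnormal, and the replacement share. The documents give neither p nor u. Assume p from 3% to 10%, u from 25% to 100%, and f from 0 to 8/15.
- Lowest: f = 0, no fall.
- Middle: 0.03 × 0.50 × 5/15 = 0.5 percentage point.
- Highest: 0.10 × 1.00 × 8/15 = 5.3 points.

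One patient in 60 is 1.7 points.

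**Weeks without a draw.** The Week 64 window opens on Day 393. Weekly retests from a Week 52 visit on Days 361-367 (study-day reading) reach it only if they last 393 − 367 = 26 to 393 − 361 = 32 days. Otherwise exit visits or other unscheduled tests fill the row. A single abnormal value there is 1/1 = 100% of patients tested, or 1/60 = 1.7% of the population. SAP 5 makes the population the default denominator.

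**The case against.** The strongest reply is that little is lost. The overall proportions, the highest and lowest value summaries, the listings, and the special-interest category for confirmed liver test elevations should keep the extremes visible. The lab-specific text in SAP 10.2 may also mean that unscheduled values were never intended for by-visit tables; the contrary reading rests mainly on a revision-history line. The trial is single-arm and descriptive, with about 60 patients.

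Most of this stands and sets the severity. It does not remove the ambiguity. The overall figure protects against loss only if it uses every on-treatment value, which the SAP does not say; built from windowed records, it would inherit the loss.

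A reader might infer more than the documents support:
- **That by-visit rates are lowered.** The counts above are replaced values, not lost abnormalities. A confirming retest leaves the triggering count unchanged. An ALC moving from 190 to 250 still counts as below 500. A worsening ALT could raise the 5x or 8x ULN counts.
- **That the 27-33% applies throughout the Extension.** Weeks 48 and 52 are ±3-day visits.
- **That recovery off drug routinely overwrites confirmed low ALC.** That needs a very early visit and a quick confirmation.
- **That the no-draw weeks show only patients with a problem.** Exits include patient withdrawal and sponsor termination, and Protocol 12.1.10 allows discretionary tests. The subset is selected, but not purely for abnormality.

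**Conclusion.** The point holds as a minor one. If unscheduled labs enter the windows as Appendix 5 says, a required retest can replace an abnormal scheduled value in by-visit tables. At a 7-day lag the exposure is 4-5 of 15 permitted days at ±7-day visits and 0-1 of 7 at ±3-day visits; at the 14-day limit for ALT/AST it is 1-2 of 15 and none. Reading these shares as probabilities assumes visit days spread evenly over the permitted range, which the documents do not state. The effect on a rate also depends on how many retests have recovered. Under the assumed ranges it runs from nothing to 5.3 points, with about half a point in the middle case.

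Overall and highest/lowest summaries should be unaffected, provided that overall means any on-treatment value.

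The no-draw weeks are a separate defect and need no assumption about lag. The alternating blanks at Weeks 64, 88, 112 and 136 recur in the hematology, chemistry and urinalysis rows. The Week 160 blank should be checked against the original table.

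**What to change.** Amend SAP 5.5.3 and 10.2 so that they agree:

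1. For by-visit lab means and threshold proportions, use the protocol-scheduled draw whenever the window holds one, so that a retest cannot replace it.
2. Tabulate hematology and chemistry by visit only at weeks where Protocol Tables 2 and 3 schedule them, with patients tested as the denominator.
3. Define overall threshold incidence as the worst on-treatment value, including unscheduled and early termination draws, so that no abnormal value is lost.

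The worst value in each window could be added as a secondary display. It is a poor main rule: the Week 24 window covers Days 99 to 210, which is 210 − 99 + 1 = 112 days, so it would give a maximum over a long period and weigh more heavily on patients tested more often.

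The cost is SAP wording, a derivation flag and fewer by-visit columns. No new data are needed. By-visit abnormality rates may look slightly less favourable.

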- ⁱ Week 12 colonoscopy should be performed either on day of visit or no more than 7 days prior to the visit date.
- ^j Colonoscopy does not need to be performed at the Early Term visit if one was completed within 8 weeks of the Early Term visit.
- ^k Enterocutaneous and perianal fistula drainage assessment will only be performed on patients with fistulas at baseline.
- ^l Blood samples for PK evaluation are to be taken up to 15-30 minutes prior to investigational drug administration (pre-dose) and just prior to discharge from the clinic (6-8 hours post-dose) on Day 1. Blood samples at subsequent visits will be trough level, taken just prior to investigational drug administration. The actual time of investigational drug administration for all visits with PK evaluation will be recorded. The blood sample at the 30-day and 90-day Safety Follow-Up Visit can be collected at any point during the visit. An additional PK sample will be obtained for patients with any AE resulting in discontinuation or SAE.
- ^m Week 12 flow cytometry analysis will only be performed for patients with a baseline sample (Day 1).
- ⁿ Prior to first dose of investigational drug, a 12-lead ECG will be performed. After the dose, patients will have hourly vital signs recorded at 1, 2, 3, 4, 5, and 6 hours post-dose. A second 12-lead ECG will be performed at the end of the observation period.

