If any of the following criteria are met, additional extended monitoring (described below) should be instituted until the finding has resolved. Baseline and hourly vital signs measurements (Hours 1 through 6) should be used to assess pulse (criteria 1 and 2 below) and ECG should be used to assess for AV block and QTcF interval (criteria 3 and 4 below).

1. The pulse 6 hours post-dose is < 45 bpm
2. The pulse 6 hours post-dose is at the lowest value post-dose (suggesting that the maximum PD effect on the heart may not yet have occurred)
3. The ECG 6 hours post-dose shows new onset second degree or higher AV block
4. The ECG 6 hours post-dose shows a prolonged QTcF interval (> 450 msec for males, > 470 msec for females)

Should post-dose symptomatic bradycardia occur, the treating physician should be notified and he or she should initiate appropriate management, begin continuous ECG monitoring, and continue observation until the symptoms have resolved.

Should a patient require pharmacologic intervention for symptomatic bradycardia, continuous overnight ECG monitoring in a medical facility should be instituted, and the first dose monitoring strategy should be repeated the following day (Day 2). The first dose monitoring strategy should also be repeated at the times specified in [Table 2](#) at Day 5 or Day 8 if any cardiac safety issues were observed on the previous Day of dose escalation (see [Table 2](#)).

Patients should have written instruction on when to return to the clinic and a 24-hour contact phone number to call in the event of any new or warranted symptoms (eg, chest pain, dizziness, palpitations, syncope, nausea, vomiting). Patients should be instructed not to drive on the same day after the first dose of investigational drug administration.

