13.2. Statistical Methods

13.2.1. General Considerations

All efficacy and safety data will be listed by patient and summarized. Baseline is defined as the last observed measurement prior to the Induction Period Day 1 receipt of investigational drug.

In general, descriptive summaries will be presented for the efficacy and safety variables collected. Continuous variables will be summarized using number of patients (n), mean, standard deviation (SD), median, minimum, and maximum. Categorical variables will be summarized using frequency counts and percentages.

There will be no imputation for missing efficacy or safety observations

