10.4. Electrocardiogram

The following ECG values will be included for summarization:

- QTcB – Bazett’s Correction
- QTcF – Fridericia’s Correction
- PR Duration
- QRS Duration
- QT Duration
- RR Duration
- Ventricular Rate

QTcF is the primary measure of corrected QT, with Bazett’s correction serving as a supportive measure. For all ECG measurements, actual values and change from baseline will be summarized continuously by visit.

The proportion of patients with ECG outliers will be presented overall and by visit. For this analysis, the categories defined below will be used:

- QT > 480 milliseconds (ms), QT > 500 ms, Female: QTcF > 470 ms, and Male: QTcF > 450 ms
- PR < 120 ms, PR > 200 ms

The interpretation of ECG results will be presented by visit (‘Normal’, ‘Abnormal, not clinically significant’, ‘Abnormal, clinically significant’).

ECG abnormalities upon first dose of study drug will be summarized categorically, with the types of abnormalities sorted alphabetically within each time point.

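### SAP Table 4 gives the 6-hour first-dose ECG no by-visit time point and would report repeat-monitoring ECGs from Days 2, 5 or 8 as Week 4

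*SAP*

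**What the plan says.** **Windows.** SAP 5.5.3 opens: "The analysis time point assignment for the post-baseline visits will be assigned based on the analysis windows described in" Table 4. It lists 12-lead ECG and vital signs among the items covered. Table 4 nevertheless has a Baseline row (day 1 or earlier). The next row is Week 4, Days 2 to 42, with target Day 29. Within a window, "If multiple assessments are available within a range, then the one closest to the target day will be used for that analysis time point". Same-day readings are averaged, "except for the lab and ECG data for which the assessment at a later time of the same day will be used".

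**Baseline.** SAP 5.5.1 says that, unless specified otherwise, "baseline is defined as the last observation collected on or before the receipt of first dose of Investigational Product (IP"). Protocol 13.2.1 says: "Baseline is defined as the last observed measurement prior to the Induction Period Day 1 receipt of investigational drug".

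**ECG collection.** Protocol Table 2 schedules ECGs at Screening, Day 1, Week 12 and Early Termination, and none at Week 4 or Week 8. Footnote n places one ECG before the first dose and adds: "A second 12-lead ECG will be performed at the end of the observation period". That period is 6 hours. Protocol 12.1.9 repeats the first-dose monitoring on Day 2 after drug treatment for symptomatic bradycardia, and also "at Day 5 or Day 8 if any cardiac safety issues were observed on the previous Day of dose escalation". Protocol 12.1.3 likewise provides for conditional ECGs on Days 5 and 8.

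**ECG analysis.** SAP 10.4 states: "For all ECG measurements, actual values and change from baseline will be summarized continuously by visit". Outliers are shown overall and by visit, and there is a categorical summary of ECG abnormalities at first dose. No Hour 6 time point is named for the continuous or by-visit outlier tables. For vital signs, SAP 10.3 fixes the baseline as the lowest pre-dose Day 1 value and tabulates hourly Day 1 values and changes.

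**The concern.** Bradycardia and conduction abnormality are adverse events of special interest, and protocol 9.2 justifies the 7-day escalation by its effect on heart rate. The ECG at Hour 6 is the planned look at conduction and repolarisation after the first dose. A reader would expect its QTcF, PR and ventricular-rate changes in the ECG tables. The windows leave it no post-baseline slot there.

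A row headed Week 4 will be taken to describe patients about four weeks into treatment. If its only ECGs were taken during or just after escalation, in patients monitored again because of cardiac findings, the label is wrong and the group is selected.

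Finally, two passages select different Day 1 ECGs as baseline if the windows are programmed by date. Every later ECG change depends on that choice, so it should be settled in the text.

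**Working it through.** The plan gives no figure to reproduce here. The check applies its own rules to its own schedule.

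**Step 1: the two Day 1 ECGs.** SAP 5.5.2 sets study day = measurement date − first dose date + 1. Both ECGs are on the first dose date, so both have study day 0 + 1 = 1 and fall in the Baseline row (≤ 1). The first post-baseline window starts at Day 2, so the Hour 6 ECG belongs to no post-baseline window.

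**Step 2: which one is baseline.**
- Table 4 Baseline row plus the later-time rule for ECG: the Hour 6 ECG.
- SAP 5.5.1 and protocol 13.2.1: the pre-dose ECG.

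The rules disagree. SAP 10.3 settles the matter for vital signs; SAP 10.4 has no matching sentence for ECG.

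**Step 3: where the Hour 6 ECG is reported.**

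| Output | Hour 6 ECG included? |
|---|---|
| Continuous values and changes by visit (10.4) | No time point |
| Outliers by visit (10.4) | No time point |
| Outliers overall (10.4) | Not stated |
| First-dose abnormality summary (10.4) | Yes, categorical |
| Extended-monitoring summary (10.3, using protocol 12.1.9) | Yes, for new second-degree or higher AV block and QTcF > 450 ms (men) or > 470 ms (women) |
| Listings (SAP 5) | Yes |

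The gap is the continuous Hour 6 change in QTcF, PR and rate, and a labelled Hour 6 row for the outliers.

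**Step 4: repeat-monitoring ECGs.** Distance to target is |day − 29|:
- Day 2: |2 − 29| = 27
- Day 5: |5 − 29| = 24
- Day 8: |8 − 29| = 21

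All three lie within Days 2 to 42. The SAP revision history (version 1.5) includes unscheduled and early-termination visits in all windows. With no Week 4 ECG scheduled, any one of these becomes the patient's Week 4 ECG unless another in the window is nearer Day 29. If all three exist, Day 8 is kept and Days 2 and 5 drop out.

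**Step 5: vital signs on the same days.** Table 2 does schedule these at Week 4, Day 28 ± 3, that is Days 25 to 31. The largest distance to target is |25 − 29| = 4. Since 4 < 21, the scheduled visit is chosen. The Day 2/5/8 readings leave the by-visit table and are not relabelled; they would become Week 4 only if no nearer reading existed.

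**Step 6: share of the schedule.** A patient who completes Induction has two scheduled on-drug ECGs in that period, Hour 6 and Week 12. The by-visit tables have a place for one of the two.

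**The case against.** The strongest reply is that the first-dose cardiac effect is well covered elsewhere. SAP 10.3 gives hourly Day 1 heart rate and blood pressure against a pre-dose baseline, heart-rate categories by hour with the overall minimum, and a table and listing of patients needing extended monitoring. That summary uses the same QTcF limits by sex as the outlier table. SAP 10.4 adds the first-dose abnormality summary, and all safety data are listed. The heart-rate and blood-pressure rationale for escalation is therefore addressed on Day 1. This stands: a reader might infer that the cardiac effect of escalation is lost, and the documents do not support that. None of these outputs, however, clearly gives a continuous Hour 6 ECG change.

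A reader might also infer that the plan makes an on-drug ECG the baseline. It does not. Both baseline definitions exclude a post-dose reading, SAP 5.5.3 limits its windows to post-baseline visits, and protocol 12.1.9 treats the pre-dose ECG as the comparator for the post-dose one. What remains is a Table 4 row that conflicts with those definitions if programmed by date, and the opening qualifier of 5.5.1 leaves room to read 5.5.3 as an exception.

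It is also fair to say that repeat monitoring is conditional, that its frequency is not given, and that the table shells, which might omit a Week 4 ECG row, are not in these documents. The trial is descriptive, with no hypothesis tests. These points limit the size of the problem; the windowing rule still says what it says.

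**Conclusion.** The point holds as a specific gap in the ECG analysis rules. For all of about 60 dosed patients, the Hour 6 ECG has no by-visit time point, and continuous first-dose changes in QTcF, PR and rate are not clearly specified. Conditional Day 2/5/8 ECGs would be reported as Week 4, for an unknown and probably small number of patients selected for cardiac findings. This assumes that Table 4 is applied as written and that no other ECG lies nearer Day 29.

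The ECG baseline is a conflict to resolve. The better reading is that SAP 5.5.1 governs, so the documents do not show that later ECG changes will be misstated. Day 2/5/8 vital signs are normally dropped from the by-visit table and not mislabelled.

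Separately, protocol 12.1.9 refers to Table 2 for the Day 5 and Day 8 repeats, and Table 2 has no column for either day. The reference may mean only the hourly schedule in footnote n, but the passages must be reconciled.

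**What to change.** In SAP 5.5.3 and 10.4:

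1. State that only pre-dose ECGs can serve as baseline, as 10.3 already does for vital signs.
2. Add Day 1, Hour 6 as an ECG time point in the continuous change and outlier tables, and say whether it counts in the overall outlier proportion.
3. Exclude Day 2/5/8 repeat-monitoring ECGs and vital signs from the Week 4 window and show them under their own label.

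Limit item 3 to the repeat-monitoring records. Starting the Week 4 window later for everything in Table 4 would leave other Day 2 to 8 results, such as unscheduled laboratory tests or early-termination assessments, without a window.

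Reconcile protocol 12.1.9 with Table 2 on the Day 5 and Day 8 repeats.

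The cost is a few sentences and some extra table rows, using data already collected. The Day 2/5/8 rows will rest on few patients and should be read as descriptive.
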